9.4 Statistical Analyses

9.4.1 General Approach

This is a double-blind placebo controlled randomized trial testing a superiority hypothesis with a two-sided type I error rate of 5%. Secondary hypotheses have been ordered according to relative importance, with one key secondary hypothesis highlighted. These will be described according to the appropriate summary statistics (e.g., proportions for categorical data, means with 95% confidence intervals for continuous data, median for time-to-event data).

A statistical analysis plan will be developed and filed with the study sponsor prior to unblinding of study and database lock.

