9.4.7 Sub-Group Analyses

Subgroup analyses for the primary outcomes will evaluate the treatment effect across the following subgroups: geographic region, duration of symptoms prior to enrollment, baseline disease severity (stratification variable of mild/moderate and severe, as well as ordinal scale of 4/5 vs 6/7) age, race, sex and comorbidities. A forest plot will display confidence intervals across subgroups. Interaction tests will be conducted to determine whether the effect of treatment varies by subgroup.

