4.2.3. Method of Assigning Subjects to Treatment Groups (Randomization)

Enrollment and randomization of subjects is done online using the enrollment module of Advantage eClinical[®].

Eligible subjects will be randomized and assigned in a 1:1 ratio to either baricitinib + remdesivir or remdesivir, with stratification by site and disease severity by ordinal scale (Moderate disease [4 or 5 on the ordinal scale] or Severe disease [6 or 7 on the ordinal scale]). The randomization is based on a variable blocked scheme to provide an approximately balanced allocation to the treatment groups during the study. If arms are added or removed later in the study, randomization will continue in an equal allocation manner.

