5. SAMPLE SIZE CONSIDERATIONS

Sample Size for Primary Analysis

The log-rank test will be used to compare treatment arms with respect to time to recovery. For the log-rank test, the two key determinants of power are the total number of events (i.e., recoveries) E and the treatment-to-control ratio of the rate of recovery. The number of events required for power $1 - \beta$ to detect a recovery rate ratio of θ using a two-tailed test at $\alpha=0.05$ is approximately

$$E = \frac{4(1.96 + z_{\beta})^2}{\{\ln(\theta)\}^2},$$

where z_{β} is the $100(1 - \beta)$ th percentile of the standard normal distribution.

The force of recovery (sometimes loosely referred to as the “recovery ratio”) is the analogue of the hazard ratio and the term “recovery rate ratio” is the analogue of the hazard ratio in this setting. A recovery rate ratio of 1.31 was reported in Cao, Wang, Wen et al. (2020) for a lopinavir/ritonavir trial that used time to improvement by 2 categories as primary endpoint. A preliminary review of data from ACTT-1 demonstrated a recovery rate ratio 1.312. It is unlikely the second component of treatment will have a similar effect size. Therefore, a recovery ratio of 1.25 is assumed for this trial. A total of 723 recoveries are needed for a recovery ratio of 1.25 with 85% power. The study will accrue until approximately 723 recoveries have been achieved. The date of study closure will be estimated based on enrollment rate and recovery/enrollment percentages. If approximately 70% of participants recover, the total sample size will be 1032.

See Section 9.2 of Appendix B of the study protocol for discussions on the sample size calculations for the key secondary outcome.

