8. EFFICACY EVALUATION

8.1. Primary Efficacy Analysis

8.1.1. Primary Analyses

The primary analysis uses the stratified log rank test to compare treatment to control through Day 29 with respect to time to recovery, as defined in Section 3.3. Stratification is based on moderate versus severe disease at baseline. As noted in Section 3.3, all deaths within 29 days will be considered censored at Day 29 with respect to time to recovery. Conceptually, a death corresponds to an infinite time to recovery, but censoring at any time greater than or equal to Day 29 gives the same answer as censoring at Day 29; both correspond to giving deaths the worst rank.

Let MM and S denote the Moderate and Severe subgroups, respectively. The z-score associated with the stratified log rank test is

$$Z = \frac{\sum_{MM}(O_i - E_i) + \sum_S(O_i - E_i)}{\sqrt{\sum_{MM} V_i + \sum_S V_i}}$$

The sums are over recovery times t_i in the moderate and severe subgroups, O_i is the number of treatment arm participants recovering at time t_i , and E_i and V_i are the null expected value and variance of the number of treatment recoveries calculated using the hypergeometric distribution. Specifically, if n_{Ti} and n_{Ci} denote the numbers of patients 'at risk' in the two arms in a given stratum at t_i , and r_i is the total number of recoveries at t_i , then $E_i = r_i n_{Ti} / (n_{Ti} + n_{Ci})$ and $V_i = r_i (n_i - r_i) n_{Ti} n_{Ci} / [n_i^2 (n_i - 1)]$, where $n_i = n_{Ti} + n_{Ci}$. The O_i , E_i , and V_i are computed separately within the moderate and severe strata.

As noted in Section 6.6.2, to maintain an overall two-sided type-I error rate of 0.05, the Lan-DeMets spending function analog of the O'Brien-Fleming boundary will be used to derive the cumulative error spending and boundaries for the interim analysis.

For the final analysis, the log rank test will be performed using the pseudocode provided in Section 6.1. The following pseudocode can be used to compute the bounds for the final analyses and compare to the calculated log-rank statistic. The Boundaries dataset will contain the updated boundaries calculated from the interim analyses using the actual information levels observed at the interim analysis.

```

data Params_LogR;
  set logrankp(rename=(Statistic=Estimate));
  if Variable='TreatmentVariable';
  _Scale_='Score';
  _Stage_= AnalysisNumber;
  keep Variable _Scale_ _Stage_ StdErr Estimate;
run;

proc seqtest Boundary=Boundaries

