8.1.2. Supplemental and Sensitivity Analyses

For all supplemental and sensitivity analyses of the primary outcome, p-values may or may not be reported, and 95% confidence levels will be used for confidence interval estimates.

The primary analysis will be repeated in the As Treated analysis population where subjects who are not treated will be censored at enrollment. The tabular and graphical summaries described in the previous section will be replicated for this As Treated analysis.

Sensitivity analyses will be performed using Cox proportional hazards models to estimate the hazard ratio. First, an ITT analysis will be performed in which subjects who die prior to recovering are treated as experiencing a competing risk in the Fine-Gray proportional hazards regression model. Second, a Cox model will be fit with binary indicators for treatment group and disease severity Moderate vs. Severe [separate models for randomized stratum and actual stratum] as well as a treatment * disease severity interaction term. The models will be fit to the ITT analysis population. The treatment group hazard ratios and CIs will be reported for both sets of models and the interaction term p-value will be reported for the interaction models. As requested by the DSMB, a restricted mean survival time analysis will be performed as an exploratory analysis. The restricted mean recovery time estimates will be provided for each treatment group and randomized disease severity stratum as well as the difference in restricted mean recovery time between treatment groups within each of the severity strata (Table 18). Time to recovery will also be explored within prior Remdesivir treatment subgroups (Any Treatment vs. No Treatment) (Table 19).

The primary analysis will also be repeated using the other subgroups defined in Section 6.4 in place of disease severity. Each subgroup will be considered separately and the tabular and graphical summaries described in the previous section will be replicated for each subgroup. The tabular summary will also include results from an analysis of time to recovery controlling for age

and duration of symptoms as continuous covariates and baseline d-dimer and CRP values as continuous covariates. A forest plot will be generated to display the overall treatment hazard ratio estimate and CI from each of the within-stratum analyses (Table 20 and Table 21). These analyses will be performed in the ITT and As Treated populations.

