The “Disease Severity” and “Analysis Population” columns will be removed. A “Subgroup” column will be inserted to the left of the “Treatment Group” column. These tables will not display the “Any...” rows. For the analysis controlling for age, symptom duration, d-dimer, and CRP values as continuous covariates, the elements for the “Subgroup” column will state “Baseline Predictors as Continuous Covariates”. The elements for the “n” and “Median Time to Recovery” columns will display “-“. P-values will not be included in these tables.

Programming Notes for Tables 22 and 23:

P-values will not be included in these tables.

Table 22 will include a column to the left of the “n” column titled “m”. The corresponding footnote will read “m = Number of subjects readmitted for COVID-19.” Table 11 will include the following footnote: “In this analysis, subjects that recover and are subsequently readmitted for COVID-19 are censored at 28 days”.

Table 23 will include a column to the left of the “n” column titled “m”. The corresponding footnote will read “m = Number of subjects reporting use of the medication of interest.” For Table 12, the “Analysis Population” column will be replaced by a column labeled “Medication of Interest”. Separate models will be fit for the following categories of medications (see Section 6.4):

- Any Medication of Interest
- Hydroxychloroquine/Chloroquine
- Corticosteroids
- Anti-Inflammatory Drugs

The table will include the following footnote: “In this analysis, subjects that reported use of the specified medications of interest (Section 6.4 of the SAP) are censored at time of medication receipt.”

Table 24: Summary of Recoveries and Deaths by Day 29 – ITT Population

Grouping Variable	Subgroup	Treatment Group	Recovered		Did Not Recover		Deaths		Not Recovered or Died	
			n	%	n	%	n	%	n	%
Disease Severity	Moderate	Baricitinib + RDV (N=X)	x	x	x	x	x	x	x	x
		Placebo + RDV (N=X)	x	x	x	x	x	x	x	x
	Severe	Baricitinib + RDV (N=X)	x	x	x	x	x	x	x	x
		Placebo + RDV (N=X)	x	x	x	x	x	x	x	x
	Any Severity	Baricitinib + RDV (N=X)	x	x	x	x	x	x	x	x
		Placebo + RDV (N=X)	x	x	x	x	x	x	x	x
Repeat for duration of symptoms categories in Section 6.4										
N= Number of subjects in the ITT Population.										

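### Time-to-recovery subgroup analyses drop severity as a stratifier, and the protocol's interaction tests reach the SAP only for severity and baseline ordinal score

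*SAP*

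**What the plan says.** The primary analysis in SAP 8.1.1 is a stratified log-rank test: "Stratification is based on moderate versus severe disease at baseline". Severity is also a randomization stratum, with site (SAP 4.2.3), and the all-severity hazard ratio in Table 15 comes from the stratified Cox model.

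For subgroups, SAP 8.1.2 says: "The primary analysis will also be repeated using the other subgroups defined in Section 6.4 in place of disease severity". Each subgroup is taken separately, and a forest plot shows the resulting hazard ratios and intervals. The programming notes for Tables 20 and 21 remove the disease-severity column and the all-subjects rows, and add: "P-values will not be included in these tables". Nothing says that severity stays as a stratifier inside the region, symptom-duration, race, comorbidity, age or sex subgroups.

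Protocol Appendix B 9.4.7 lists region, symptom duration, baseline severity, age, race, sex and comorbidities, and then commits: "Interaction tests will be conducted to determine whether the effect of treatment varies by subgroup". For time to recovery, the SAP specifies interaction models with a reported p-value for treatment by severity (randomized and actual, Table 16) and treatment by baseline ordinal score (Table 17). It specifies no others.

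**The concern.** There are two separate issues.

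First, a hazard ratio that ignores a strong prognostic factor estimates a different quantity from one stratified by that factor. With the same true effect in every patient, the unstratified subgroup ratios lie on average closer to 1 than the severity-stratified primary ratio. A chance difference in severity mix between arms inside a subgroup also passes directly into that subgroup's estimate. A reader who sets age or race subgroups against the primary result would be comparing unlike quantities.

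Second, for most factors the protocol's promised test of effect modification has no counterpart in the SAP. Readers are left to compare separate within-level intervals, which is not a test of whether the effects differ.

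**Working it through.** **1. The plan's own figures.** SAP section 5 states: "A total of 723 recoveries are needed for a recovery ratio of 1.25 with 85% power". Its formula is E = 4(1.96 + z)² / (ln θ)². With z rounded to 1.04 and θ = 1.25, E = 4 × 3.00² / 0.2231² = 723. Unrounded z gives 721.3, or 722 recoveries. The SAP adds: "If approximately 70% of participants recover, the total sample size will be 1032", and 723 / 0.70 = 1032.9. Both figures reproduce, and neither is disputed here.

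**2. Subgroup definitions without an interaction test.** From SAP 6.4, leaving out severity and ordinal score: region 2, symptom duration 3, race 1, comorbidities 3, age 1, sex 1. The total is 11.

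**3. Shift from leaving out severity.** The documents give no recovery rates by severity stratum, so these are assumptions shown over a range: 67% moderate, exponential recovery, a common ratio of 1.25 in both strata, 1:1 allocation, censoring at 28 days. For stratum s the control rate is λₛ = −ln(1 − Rₛ)/28, where Rₛ is 28-day recovery. With Sₐ and fₐ the survival and density of arm a mixed over severity, the limiting unstratified log hazard ratio b solves

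∫₀²⁸ { f₁ − (f₀ + f₁) · eᵇS₁ / (eᵇS₁ + S₀) } dt = 0.

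| Control recovery, moderate/severe | Control recovery overall (0.67/0.33 mix) | Limiting HR | Shift, ln(1.25/HR) | Share of log HR lost |
|---|---|---|---|---|
| 75% / 60% | 70% | 1.245 | 0.004 | 2% |
| 80% / 50% | 70% | 1.230 | 0.016 | 7% |
| 85% / 40% | 70% | 1.206 | 0.036 | 16% |
| 90% / 40% | 74% | 1.190 | 0.049 | 22% |
| 95% / 30% | 74% | 1.150 | 0.083 | 37% |

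Stratifying by severity returns 1.25 in every row. All rows give overall control recovery of 70% to 74%, so the plan's 70% cannot say which applies. With equal recovery in the two strata, or a true ratio of 1, there is no shift.

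**4. Comparison with sampling error.** The standard error of a subgroup log hazard ratio is about √(4/(723f)), where f is the subgroup's share of recoveries. For f = 0.5 it is √(4/361.5) = 0.105. For f = 0.2 it is √(4/144.6) = 0.166. Every shift in the table is smaller than both.

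**5. Noise in a single trial.** Simulated root-mean-square difference between the severity-stratified and unstratified log hazard ratios (this includes the mean shift):
- Sharp contrast (68% moderate, recovery 89%/31%), simple randomization within the subgroup: about 0.15 at n = 150 and 0.11 at n = 300.
- Same contrast, arms balanced within severity: about 0.09 and 0.07.
- Recovery 80%/50%, arms balanced within severity: about 0.04 and 0.03.

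The standard error is about 0.19 at n = 150 and 0.14 at n = 300.

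**6. What the missing tests could detect.** For a two-level factor, SE = √(4/(723f) + 4/(723(1−f))).
- Split 50/50: SE = 0.149. Power for a ratio of hazard ratios of 1.25 is Φ(0.2231/0.149 − 1.96), about 32%. The ratio detectable with 85% power is exp(0.149 × 2.996), about 1.56.
- Split 20/80: SE = 0.186. Power for 1.25 is about 22%, and the ratio detectable with 85% power is about 1.75.

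**The case against.** The strongest reply is that these are exploratory analyses and the choices can be defended. Protocol 9.4.7 does not require severity stratification within subgroups. An unstratified hazard ratio is a legitimate marginal quantity, and small subgroups can leave sparse strata. Effect variation by severity is examined separately, by stratum and by ordinal score. Any attenuation acts in the same direction on all levels of a factor, so contrasts between levels are largely kept unless severity mix differs across levels. The simple-randomization figures also overstate imbalance for the two region definitions: randomization is stratified by site and severity, and a region is a union of sites. All of this stands. It makes the point modest but does not remove it, because the subgroup ratios still differ in kind from the primary ratio they will be compared with.

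The note removing p-values from Tables 20 and 21 could be read as a ban on interaction tests. It is better read as dropping the log-rank column inherited from Table 15. SAP 8.1.2 leaves p-values for supplemental analyses optional. That permits interaction tests but does not prespecify them, so the mismatch with the protocol remains. Low power is a reason for a cautious label, not for leaving a protocol commitment unmet without comment.

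**Conclusion.** Both issues hold, at modest size. Severity is dropped as a stratifier in the non-severity subgroup analyses of time to recovery. Under the stated assumptions a true ratio of 1.25 would tend to appear as about 1.15 to 1.245, depending on how prognostic severity is. The mean shift is generally smaller than subgroup sampling error. Only in small subgroups with a sharp severity contrast does the change in a single estimate approach that error. The protocol's interaction tests are missing from the SAP for 11 subgroup definitions.

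A reader might infer more than the documents support:
- That interaction tests are omitted altogether. They are specified, with reported p-values, for severity and baseline ordinal score.
- That subgroup differences cannot be judged. Hazard ratios and intervals are tabulated and plotted by level, which allows a rough comparison. What is missing is a formal test.
- That attenuation of a known size is certain. It needs stratum-specific recovery rates that the documents do not give. It does not arise from severity mixing in the severity or ordinal-score subgroups, since each score lies in one stratum.
- That the trial's main test loses power. The primary test stays severity-stratified, and Tables 20 and 21 show no all-subjects row.

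**What to change.** In SAP 8.1.2, state that within each non-severity subgroup the Cox model and log-rank test remain stratified by randomized disease severity.

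For each remaining factor (region, symptom duration, race, comorbidities, age, sex), fit one severity-stratified Cox model with treatment, factor and treatment-by-factor terms, using a joint test where the factor has more than two levels. Report the interaction p-value in a footnote to Table 20, as is done for Tables 16 and 17, labelled exploratory and unadjusted. If the sponsor does not want these tests, amend Protocol Appendix B 9.4.7 to match the SAP.

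The cost is SAP wording and a few lines of code, with no new data and no effect on the primary test. Small subgroups with sparse strata lose a little information. The interaction tests have low power, so a non-significant result must not be read as evidence of a uniform effect. If all 11 definitions are tested at 5%, about 11 × 0.05 = 0.55 false positives are expected when no effect modification exists, which is why the exploratory label matters.

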3.3.2. Recovery and Time to Recovery

The primary efficacy outcome measure is the time to recovery. Recovery will be defined as having a value of 1, 2, or 3 on the clinical status 8-point ordinal scale. The time to recovery will be defined as the elapsed time (in days) from randomization to the earliest day at which a subject

reaches recovery. Note that since clinical status assessments are recorded as defined in Section 4.3, the day that is being assessed (not necessarily the day the response is collected) will be used to determine the timing of events. For example, a subject with a score of 5 recorded on Days 1 - 3 and a score of 3 recorded on Day 4 will have a time to recovery equal to 3 days. It is also possible that a subject has a clinical status score > 3 reported for a particular day but was subsequently discharged on the same day. Such cases will be reviewed by the NIAID Medical Officer to make the determination of whether the subject should be considered recovered in analyses. Subject data to be reviewed as part of this determination will include the reported clinical status scores while hospitalized, where the subject was discharged to (e.g. private residence, rehabilitation facility, long-term care/nursing home), and any information regarding readmittance.

Any subjects that are lost to follow-up or terminated early prior to an observed recovery will be censored at the day of their last observed assessment. Subjects who complete follow-up but do not experience recovery will be censored at the day of their Day 29 visit. All deaths within Day 29 (and prior to recovery) will be considered censored at 28 days. Note that we do not expect many subjects to worsen after discharge.

However, we will evaluate whether any discharged subjects subsequently experience a worse clinical status and sensitivity analyses will be conducted accordingly. For these analyses, subjects who recover but are later re-admitted for COVID-19 will not be considered a recovery but will instead be censored at 28 days.

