6.4. Covariates and Subgroups

Subgroup analyses for the main efficacy outcomes (i.e. the primary and key secondary analyses) will evaluate the treatment effect across the following subgroups:

- Geographic region:
 - US sites; Non-US sites
 - North American sites; Asian sites; European sites
- Duration of symptoms prior to enrollment
 - Quartiles
 - ≤ 10 days; > 10 days
 - \leq Median; $>$ Median
- Race (White; Black/African American; Asian; Other)
- Comorbidities
 - None; Any
 - None, One, Two or more
 - Obese; Non-Obese
- Age (<40 ; 40-64; 65 and older),
- Sex (Female; Male),
- Severity of disease
 - Randomization stratification: Moderate (ordinal 4/5); Severe (ordinal 6/7).
 - Actual disease severity at baseline: Moderate (ordinal 4/5); Severe (ordinal 6/7)
Note these analyses will only be performed if at least one subject is erroneously randomized into the incorrect disease severity stratum.
 - Baseline ordinal scale category: 4; 5; 6; 7

Additionally, main analyses of all secondary efficacy outcomes will evaluate the treatment effect across the following subgroups:

- Duration of symptoms prior to enrollment (\leq Median; $>$ Median)
- Severity of disease

- Randomization stratification: Moderate (ordinal 4/5); Severe (ordinal 6/7).
- Actual disease severity at baseline: Moderate (ordinal 4/5); Severe (ordinal 6/7)

Note these analyses will only be performed if at least one subject is erroneously randomized into the incorrect disease severity stratum.

- Baseline ordinal scale category: 4; 5; 6; 7

There will also be a sensitivity analysis of the primary, key secondary, and mortality outcomes to evaluate the effect of concomitant therapy including experimental treatment and off-label use of marketed medications that are intended as treatment for COVID-19 and are given to patient prior to and during the study. A blinded review of the concomitant medication data will be performed by the medical monitor to identify medications that fall into any of the following categories of “Medications of Interest”:

- Antivirals
 - Protease inhibitors
 - Polymerase inhibitors
- Potential Treatments for COVID-19
 - Hydroxychloroquine/Chloroquine
 - Other
- Corticosteroids
- Other anti-inflammatory drugs
 - Monoclonal Antibodies Targeting Cytokines
 - Other Biologic Therapies

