Summaries of subjects who report use of the categories and subcategories of therapies/treatments will be provided. Note that after the blinded review of the medications, additional categories/sub-categories may be defined and/or categories/sub-categories may be combined.

In addition, the sensitivity analyses will consider the following categories (individually):

- Any Medication of Interest
- Hydroxychloroquine/Chloroquine
- Corticosteroids
- Other Anti-Inflammatory Drugs

For the recovery analyses, if a subject recovered prior to use of any of the medications/therapies, then the subject will still be counted as a recovery in the sensitivity analysis. For the analysis of the key secondary outcome, if a subject reports use of any of the medications/therapies prior to their Day 15 assessment, then the subject’s last clinical status score prior to medication/therapy use will be used as their Day 15 outcome. For the mortality analyses, subjects will be censored at the time of medication/therapy initiation.

In addition, the effect of treatment on the primary and key secondary efficacy outcomes will be explored via regression modeling controlling for age, duration of symptoms prior to enrollment, baseline d-dimer, and baseline CRP values as continuous covariates.

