In addition, a forest plot will be generated for the “leave one out” sensitivity analyses described in Section 6.7; hazard ratio estimates and CIs will be provided for each subgroup that leaves a single site out.

An additional sensitivity analysis will evaluate the effect of recoveries that were not sustained as indicated in Section 3.3.2.

As noted in Section 6.4, analyses that take into account concomitant medication will be performed. The primary analysis will be repeated, where subjects who take prohibited medications will be treated as treatment failures and will be censored at the time of medication use.

Two corroborative summaries will also be generated. A summary of the number and percentage of subjects in each treatment group who recovered (and are alive), did not recover (and are alive), and died by Day 29 will be summarized. The summary will also include the numbers and percentages, grouping deaths and non-recoveries together (Table 24). The summaries will also be provided by the duration of symptoms categorizations specified in Section 6.4.

Other censoring techniques and additional analyses of the primary outcome may be performed.

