If necessary, a row for “No clinical status score reported – Completed study without reporting score” will be added as the last row for each day.

Table with similar format:

Table 34: Clinical Status Scores by Treatment Group and Study Visit – As Treated Population

Table 35: Summary of Clinical Status Score by Treatment Group and Study Visit – ITT Population

Study Visit	Statistic	Baricitinib + RDV (N=X)	Placebo + RDV (N=X)	All Subjects (N=C)
Baseline	Number of reported clinical scores	x	x	x
	Mean (SD)	x.x (x.x)	x.x (x.x)	x.x (x.x)
	Median	x.x	x.x	x.x
	Range (Min, Max)	x, x	x, x	x, x
Day 3	Number of reported clinical scores	x	x	x
	Mean (SD)	x.x (x.x)	x.x (x.x)	x.x (x.x)
	Median	x.x	x.x	x.x
	Range (Min, Max)	x, x	x, x	x, x
	Change from Baseline Mean (SD)	x.x (x.x)	x.x (x.x)	x.x (x.x)
Continue for Days 5, 8, 11, 15, 22, 29				
N = Number of subjects in the ITT Population. SD = Standard deviation. Missing values were imputed using Last Observation Carried Forward. Clinical scores of 8 were carried forward from the date of death for subjects who died.				

Table with similar format:

Table 36: Summary of Clinical Status Score by Treatment Group and Study Visit – As Treated Population

Table 37: Time to Discharge or to a NEWS of ≤ 2 by Treatment Group

Analysis Population	Treatment Group	n ^a	Median Time		HR		P-value
			Estimate	95% CI	Estimate	95% CI	
ITT Population	Baricitinib + RDV (N=X)	x	x.x	x.x, x.x	x.xx	x.xx, x.xx	x.xxx
	Placebo + RDV (N=X)	x	x.x	x.x, x.x			
As Treated Population	Baricitinib + RDV (N=X)	x	x.x	x.x, x.x	x.xx	x.xx, x.xx	x.xxx
	Placebo + RDV (N=X)	x	x.x	x.x, x.x			

N= Number of subjects in the specified treatment group and analysis population.
n = Number of subjects who discharged or had a NEWS of ≤ 2 prior to Day 29.
HR is the ratio of the hazard of discharge or NEWS of ≤ 2 in each treatment group estimated from the Cox model. The ratio is Baricitinib + RDV to Placebo + RDV. P-value calculated using the Log-rank test

Tables with similar format:

Table 38: Time to Discharge or to a NEWS of ≤ 2 by Treatment Group within Subgroups – ITT Population

Table 39: Time to Discharge or to a NEWS of ≤ 2 by Treatment Group within Subgroups – As Treated Population

Programming notes for Tables 38 – 39: “Subgroup Category” and “Subgroup” columns will replace the “Analysis Population” column to the left of “Treatment Group”. Rows will be repeated for each subgroup. P-values will not be displayed in these tables.

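### The medication-use sensitivity analysis of recovery is labelled a failure analysis but censors users at use, and its rules do not work for drugs ongoing at randomization

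*SAP*

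**What the plan says.** SAP 6.4 plans a sensitivity analysis of the primary, key secondary and mortality outcomes for a list of Medications of Interest, including drugs "given to patient prior to and during the study". The rules differ by outcome:

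- **Recovery.** SAP 6.4 says only that a recovery before use still counts. SAP 8.1.2 supplies the rest: "subjects who take prohibited medications will be treated as treatment failures and will be censored at the time of medication use". The Table 23 footnote says that users "are censored at time of medication receipt" and does not mention failure.
- **Day 15 status.** SAP 6.4 says that a user's "last clinical status score prior to medication/therapy use will be used as their Day 15 outcome". Death is not excepted.
- **Mortality.** SAP 6.4 and the Table 69 footnote censor at the start of the medication.

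Elsewhere the SAP handles unfavourable outcomes differently. Deaths before recovery are censored at 28 days (3.3.2), and 8.1.1 explains that censoring at Day 29 or at any later time gives the same answer: "both correspond to giving deaths the worst rank". A recovered subject later readmitted "will not be considered a recovery but will instead be censored at 28 days" (3.3.2), and the Table 22 footnote agrees: "subjects that recover and are subsequently readmitted for COVID-19 are censored at 28 days". In the Table 35 summary, "Clinical scores of 8 were carried forward from the date of death for subjects who died".

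On use that began before randomization, the Table 54 programming note counts drugs still ongoing at enrollment, Listing 10 provides for starts before enrollment, and Protocol Appendix B 6.5.1 lets some such drugs continue. SAP 4.3 takes the first clinical status score at randomization.

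**The concern.** The sentence in 8.1.2 names one estimand and prescribes another. Counting use as failure is a composite: the user is known not to have succeeded. Censoring at use is hypothetical in type: it asks what recovery would have looked like without the drug, and it is valid only if users and non-users still at risk have the same prospects. That is doubtful here. Corticosteroids are on the list, and Protocol Appendix B 6.5.2 permits them for ARDS and shock, so use linked to poor prognosis is foreseeable. Someone who relies on the 8.1.2 text would misread what the estimate assumes and which way it may lean.

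The second problem is one of execution. The rules need a time of use after time zero, or a score before use. A subject already on a listed drug at randomization has neither, so a programmer must either drop the subject from an ITT analysis or invent a rule.

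**Working it through.** **1. The plan's own figures.** SAP 5 gives E = 4(1.96 + z)²/(ln θ)². With θ = 1.25 and z = 1.036 for 85% power, E = 721.3, against the stated 723. Then 723/0.70 = 1032.9, against the stated 1032. Both reproduce, and nothing below changes them.

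**2. What each coding does.** In 8.1.1 the expected recoveries at time t are E = r·n_T/(n_T + n_C). Under censoring at use, a user leaves n_T or n_C from that day. Under failure coding, the user stays in until 28 days and never enters r. Both codings count the same recoveries and differ only in the risk set, so they are different analyses.

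**3. How far they can differ.** The documents give no use rates, so every rate here is assumed. The simulation used N = 1032, no drug effect, medication starts uniform over Days 1-14, 28 days of follow-up, a Cox model stratified by severity, and 600 trials per cell (Monte Carlo SE 0.003). Ranges are over four set-ups for severity mix and recovery rate. The ITT hazard ratio stayed at 0.995-1.008.

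| Use, control v active (never-recoverers; others) | As written | Failure coding |
|---|---|---|
| 50 v 50; 10 v 10 | 0.997-1.003 | 0.998-1.004 |
| 30 v 20 in all | 0.999-1.007 | 1.063-1.073 |
| 50 v 40; 15 v 10 | 0.977-0.988 | 1.029-1.039 |
| 60 v 40; 10 v 10 | 0.935-0.954 | 0.998-1.004 |
| 60 v 40; 20 v 10 | 0.957-0.965 | 1.059-1.073 |
| 80 v 50; 20 v 10 | 0.905-0.937 | 1.058-1.079 |
| 40 v 60; 10 v 10 | 1.047-1.076 | 0.996-1.005 |
| 50 v 80; 10 v 20 | 1.079-1.110 | 0.933-0.944 |

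A second model (single stratum, gamma-frailty recovery times, runs of 600,000 subjects) agrees in pattern. With no drug effect and prognosis-linked use before recovery of 8% v 4%, 17% v 8%, 25% v 13% and 32% v 17%, the hazard ratio is 0.98, 0.96, 0.92 and 0.90 as written, and 1.04, 1.07, 1.11 and 1.14 with failure coding. Where use was unrelated to prognosis (28% v 14%), the values were 0.99 and 1.19.

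**4. Use ongoing at randomization.** The censoring time is the medication start minus randomization, which is zero or negative, so the subject enters no risk set for recovery or mortality. For Day 15 the first score is taken at randomization, so no pre-use score exists. The only stated rule that censors at enrollment concerns untreated subjects in the As Treated analysis (8.1.2). As an illustration, if 10-30% were on a listed drug:

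- subjects lost: 1032 × 0.10 = 103 to 1032 × 0.30 = 310;
- recoveries left: 723 × 0.9 = 651 to 723 × 0.7 = 506;
- SE of the log hazard ratio, 2/√E: from 0.074 to 0.078-0.089.

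**5. Deaths by Day 15.** Protocol Appendix B Table 6 assumes 2-3% dead at Day 15 in scenarios 1 and 5, which is 21-31 of 1032. If 30-60% of these followed use (assumed), 6-19 deaths would enter the model with a pre-use score. A proportional odds simulation (survivors from scenario 1, severity as covariate) gave odds ratios with death kept and with death replaced of 1.006 and 1.006 (2% mortality, equal use), 0.999 and 0.998 (2%, use 70 v 50), and 0.999 and 0.990 (8%, use 70 v 50). The shift is at most about 0.01.

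**The case against.** The strongest reply is that the operation is clear. SAP 8.1.2 itself says to censor at use, Table 23 repeats it, and the mortality rule does the same, so deleting two words would cure the label. Neither coding is uniformly nearer 1.00, so a composite is a choice rather than a correction. SAP 8.1.2 allows other censoring techniques, and SAP 2.1 leaves intercurrent-event handling to a manufacturer addendum. Much of this stands, but optional extra analyses and an addendum outside these documents do not correct the text of this SAP.

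Four stronger readings are tempting and are not supported:

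- **That Table 23 tells its reader that use counts as failure.** Its title and footnote describe a medication sensitivity analysis with censoring; the failure label is only in the 8.1.2 text.
- **That Day 15 deaths will be displayed as living inpatients.** The medication rows of Table 25 show an odds ratio and interval, with no category counts. Table 33, which does show categories, has a death row and no replacement rule. Table 35 is a separate carried-forward summary, so its footnote does not contradict 6.4. Replacing every post-use score is also in keeping with the mortality rule beside it.
- **That many subjects will be lost through ongoing use.** Protocol Appendix B 6.5.1 stops COVID-directed drugs at enrollment with two exceptions, and exclusions 11, 12 and 14 narrow the pool further. The 10-30% is illustrative only.
- **That the trial's main conclusion is at risk.** The ITT log-rank test does not use these rules.

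**Conclusion.** The point holds for supportive estimates only, at minor to moderate severity. Two faults are established from the text without any assumption: the 8.1.2 label contradicts its own rule and the SAP's coding of deaths and readmissions, and the rules have no workable form for use ongoing at randomization. The missing exception for death at Day 15 is a lesser gap, with an effect of about 0.01 on the odds ratio under the assumed rates.

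The size and direction of any shift in the recovery estimate are unknown, because they depend on use rates by arm and on their link to prognosis. With equal use and no drug effect, both codings give about 1.00. Tables 23 and 69 and the medication rows of Table 25 carry no treatment p-values.

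**What to change.** - **SAP 8.1.2 and Table 23.** Remove the failure label from the censor-at-use analysis and state that it assumes non-informative censoring. Add a block in which subjects who start a Medication of Interest after randomization and before recovery are not recovered and are censored at 28 days. Label it a composite that can favour the arm with less use (null hazard ratio up to about 1.14 with prognosis-linked use under the assumed rates, and 1.19 in one cell with unrelated use), and show it beside the censored result.
- **SAP 6.4, ongoing use.** State that the rules for recovery, Day 15 and mortality are triggered only by starts after randomization. Keep subjects with use ongoing at randomization in the analysis and evaluate that use as a baseline subgroup or covariate. Give a separate ITT count, because Table 54 is As Treated and pools ongoing use with later starts.
- **SAP 6.4 and the Table 25 medication rows.** Keep deaths by Day 15 as category 8, let other users keep the pre-use score, and state this mixed rule.
- **Terminology.** Replace 'prohibited' with 'Medications of Interest' in 8.1.2, 9.1.2, and the Table 55 footnote and programming note; the list includes drugs that the protocol permits in some circumstances.

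The cost is rewording, one extra table block, the baseline-use analysis with its count, and a recoding of the Table 25 medication rows. No new data are needed. The downside is a Day 15 rule that keeps deaths after use but not improvements after use, which must be stated openly.
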